7.2 Safety Variables

All safety analyses will be performed on the SES and will be done overall and by actual dose group 20 U [for final analysis pooled over stages 1 and 2 if not stated otherwise below], 50 U, 75 U, 100 U). Analyses of AEs will be based on MP as well as the optional OLEX period, if applicable.

AEs will be coded according to the Medical Dictionary for Regulatory Activities (MedDRA, version 23.1) using the version and the update strategy as defined in the data management plan. Only TEAEs will be summarized, which are defined as AEs with onset or worsening after the first administration of IP. Incidences will be calculated for TEAEs on the system organ class (SOC) level and on the preferred term (PT) level (i.e., total and percentage, by intensity, and by relationship). Listings and (as applicable) tables displaying incidences for TEAEs leading to discontinuation, serious TEAEs, TEAEs of special interest, and deaths will also be provided. Additionally the number and percentage of subjects with at least one non-serious TEAE with incidence $\geq 5\%$ will be displayed by SOC and PT (final analysis only). Time to onset and duration of TEAEs will be listed, and a by subject listing of TEAEs related to COVID-19 pandemic will be provided.

Calculation of time to onset/duration of AEs (days):

- Time to onset of an AE is defined as start date of AE - date of first administration of study drug [+ 1 for AE starting after start of treatment]
- The duration will be calculated as stop date - onset date + 1.

If a subject has more than one outcome within a preferred term (PT) only the worst outcome will be used in the frequency tables. Also on subject level only the worst outcome category per subject will be counted in the frequency table. The worst outcome is defined in the following order:

- recovered/resolved

[figure not shown]
- recovered/resolved with sequelae
- recovering/resolving
- not recovered/not resolved
- unknown
- fatal.

In case of missing intensity or missing causal relationship of an AE the worst case principle will be applied, i.e. a missing intensity will be set to “severe” and a missing causal relationship will be set to “related”.

Laboratory evaluations and vital signs (values and changes from baseline) will be analyzed descriptively by treatment and study visit. Visits as documented in the eCRF will be used, i.e. visit “End of MP” and not “V15” will be analyzed. The same applies to analysis of TEAE incidence by time interval.

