The observation period for each subject (in stage 1 and stage 2) will be at least 180 days. Subjects who have relapsed to baseline status of their GFL based on the investigator's assessment on the FWS at maximum frown up to Day 180, should complete the End of MP study visit at Day 180. Subjects who have not relapsed to baseline status of their GFL at Day 180 (V9) will continue to be observed for up to 180 additional days. For subjects who have relapsed to baseline status of their GFL between Day 180 and Day 360 the End of MP can be performed at each of the respective Observational Visits. If no relapse to baseline status is measured, the End of MP will be performed at Day 360 (V15).

Optional OLEX:

Subjects who have relapsed to baseline status of their GFL in the MP will have the option to receive a follow-up treatment with the market approved dose of 20 U NT 201 for their GFL between Day 180 and Day 360. An OLEX Follow-Up Visit V16 will be performed 30 days after the optional injection to document the occurrence of adverse events (AEs)/ adverse events of special interest (AESIs).

Study duration for each subject (in stage 1 and stage 2) will be at least 180 days, plus the individual duration of screening (up to 14 days), plus 30 days OLEX follow-up for subjects who elect to receive an optional follow-up treatment. The overall maximum study duration will be up to 390 days in case the subject will receive an optional follow-up treatment plus the individual duration of screening (up to 14 days) for each subject.

Subjects who withdraw or are withdrawn prematurely from the study will be requested to perform the End of MP study visit. Please note that subjects who receive the optional follow-up treatment but do not attend the OLEX Follow-Up Visit V16 for any reason will not be considered as discontinued prematurely from the study.

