5 ANALYSIS SETS

The following analysis sets will be defined for the statistical analysis of this clinical study:

Safety Evaluation Set (SES)

[figure not shown]
The SES is the subset of all subjects who were exposed to study medication.

Analyses based on the SES will use the actual treatment that a subject received at Day 1 (V2) to define the treatment group.

Full Analysis Set (FAS)

The FAS is the subset of subjects in the SES for whom any efficacy variable is available (i.e., all subjects who have a baseline and at least one post-baseline value of any efficacy variable).

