6.2.1 Primary Safety Variable(s)

[figure not shown]
The primary safety variables are the occurrences of treatment emergent adverse events (TEAEs), treatment emergent serious adverse events (TESAEs), treatment emergent adverse events of special interest (TEAESIs), related TEAEs and related TESAEs by dose group for the entire study period.

[figure not shown]
An AE is considered treatment-emergent with onset or worsening on or after date of the first administration of investigational product (IP). Each documented worsening of an AE will be counted and presented as separate AE. The start date of the AE will be the date of worsening.

[figure not shown]

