7.1 Efficacy Variables

The efficacy analyses will be based on the FAS and will be done by randomized treatment group (20 U [for final analysis pooled over stages 1 and 2 if not stated otherwise below], 50 U, 75 U, 100 U). Statistical tests will be two-sided hypothesis tests for between-treatment differences in general. Continuous variables (values and changes from baseline) will be summarized by number of values analyzed (n), mean, standard deviation, median, quartiles, minimum, and maximum. [REDACTED]

[REDACTED]

[REDACTED]

[REDACTED]

For qualitative variables, absolute and percent frequencies (n, %) and, if applicable, shift tables will be displayed. Confidence limits [REDACTED] will be given, where appropriate.

[figure not shown]
[REDACTED]

[REDACTED]

[figure not shown]
Mean, first quartile (Q1), median, and third quartile (Q3) will be reported to one decimal place more than the data were collected, for the standard deviation two decimal places more will be displayed; for derived data, an adequate number of decimal places will be chosen. Percentages will be calculated using the denominator of all subjects in a specified population and treatment group. The denominator will be specified in a footnote to the tables for clarification if necessary. Percentages will be reported to one decimal place.

Efficacy analysis will be based on the MP solely, ending with the End of MP visit. (As specified in the CSP, the End of MP visit is performed between Day 180 ± 7 and 360 ± 7 , depending on when the individual subject relapsed to baseline according to the investigator's assessment on the FWS at maximum frown.) Generally, only data from visits until regular End of MP will be used for

efficacy analyses, i.e. data from erroneously performed visits after occurrence of relapse⁶ (V10 to V14 and/or from End of MP visit) will be listed only.

⁶ based on investigator's FWS scores at maximum frown

[figure not shown]

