7.2.1 Primary Safety Variable(s)

Incidence (absolute and percentage) of TEAEs, TEAESIs, TESAEs, and related TEAEs will be calculated on the level of system organ class (SOC) and preferred term (PT). In addition, incidences for TEAE will also be presented by worst intensity and by worst causal relationship. In general, incidences for TEAEs will be reported by the following actual dose groups: 20 U [pooled over stage 1 and stage 2], 50 U, 75 U, 100 U. To explore potential stage effects, incidences for TEAE by worst causal relationship will additionally be provided separately for actual 20 U dose groups from stage 1 and stage 2.¹¹

The following AE summary tables will be created by actual dose group and overall (entire study period), whereby in general the dose groups 20 U pooled, 50 U, 75 U, 100 U will be used:

- TEAEs, subjects with TEAEs and number of TEAEs by SOC and PT.

[figure not shown]
¹¹ This analysis was added after finalization of the CSP.

[figure not shown]
- TEAEs, subjects with TEAEs by PT.
- TEAEs, subjects with TEAEs and number of TEAEs by SOC and PT [REDACTED]
- Non-serious TEAEs, [REDACTED] by SOC and PT.
- TEAEs by worst intensity, subjects with TEAEs.
- TEAEs by worst causal relationship, subjects with TEAEs (20 U stage 1, 20 U stage 2, 20 U pooled, 50 U, 75 U, 100 U).
- Treatment related TEAEs by SOC and PT.
- Treatment related TEAEs occurring between baseline and Day 180 (V9 or End of MP), by SOC and PT.
- Treatment related TEAEs occurring between baseline and End of MP, by SOC and PT.
- TEAEs by worst outcome, subjects with TEAEs.
- TESAEs, subjects with TESAEs by SOC and PT.
- TESAEs, listing of subjects.
- Related serious TEAEs, listing of subjects.
- Deaths, listing of all serious TEAEs leading to death.
- TEAEs leading to discontinuation, listing of subjects.
- TEAESIs, subjects by SOC and PT.
- TEAESIs, listing of subjects

[figure not shown]
Related TESAEs, deaths, TEAEs leading to premature discontinuation and TEAEs related to COVID-19 will be listed only.

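### Final safety tables by Day 1 dose mix relapse-dependent follow-up with events after the 20 U OLEX injection, with no visible Day 180 or post-OLEX split for TESAEs and TEAESIs

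*SAP*

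**What the plan says.** **What is counted, and under which dose.** SAP 7.2 says "Analyses of AEs will be based on MP as well as the optional OLEX period, if applicable". SAP 7.2.1 opens its list of outputs with "The following AE summary tables will be created by actual dose group and overall (entire study period"), using pooled 20 U, 50 U, 75 U and 100 U. SAP section 5 adds: "Analyses based on the SES will use the actual treatment that a subject received at Day 1 (V2) to define the treatment group". SAP 6.2.1 counts an event as treatment-emergent from the first administration, and no second clock starts at the OLEX injection. Protocol 12.3.5.1 defines the primary safety variables over the whole study, so the SAP follows the protocol here.

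**How long subjects are followed.** Under SAP 3.1, subjects who relapse by Day 180 finish the main period then; the others "will continue to be observed for up to 180 additional days". SAP 7.1 says that the End of MP visit is timed "depending on when the individual subject relapsed to baseline". Under Protocol 10.1, AE collection stops at End of MP or, after an OLEX injection, at V16, which is 30 days later.

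**Which tables have a window.** SAP 7.2.1 lists "Treatment related TEAEs occurring between baseline and Day 180 (V9 or End of MP), by SOC and PT" and a companion table to End of MP, both for related events only. In a remark about visit labels, SAP 7.2 notes "The same applies to analysis of TEAE incidence by time interval"; no interval limits are visible. The third TEAE bullet in 7.2.1 ends in a redaction. The stage 1 interims (SAP 7.4.2) tabulate TEAEs, TEAESIs, TESAEs and related TEAEs, but exclude stage 2.

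**The concern.** Safety by dose is half of the primary objective, and Protocol 12.4.5 rules out inferential methods for safety. Readers will therefore compare the tabulated percentages directly. Two features of those percentages depend on the efficacy outcome rather than on the Day 1 dose:

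- A longer-acting dose keeps subjects under observation longer and collects more background events.
- A dose with more relapsed subjects has more of them eligible for a second injection, and the events after it are booked to the Day 1 dose.

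The two pull in opposite directions, so a reader cannot correct for them by eye. TEAESIs are the events thought possibly to indicate toxin spread (Protocol 10.3). One that follows a 20 U OLEX injection but appears under 100 U blurs the comparison that the top dose was added to provide. The interims cannot help, because they contain neither 100 U nor the stage 2 20 U subjects.

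**Working it through.** **1. Follow-up lengths from the documents.** The stated maximum reproduces: 360 + 30 = 390 days, excluding screening. Planned AE follow-up is 180 days (relapse by Day 180, no OLEX), about 210 (the same with OLEX at Day 180), up to 360 (no relapse) and up to 390 (late relapse with OLEX). The ratio of longest to shortest is 390/180 = 2.17.

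**2. Assumptions for the size.** The documents give no AE rates, durations by dose or OLEX uptake. Assumed here:
- Median duration 150/180/210/230 days for 20/50/75/100 U; Weibull relapse times with shape 2.5, rounded up to 30-day visits.
- No dose effect on AEs.
- 50% OLEX uptake among subjects relapsed by Day 360.
- Main-period follow-up equal to the relapse visit, bounded to 180 to 360 days.

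A simulation of 1,000,000 subjects per dose then gives mean main-period follow-up of about 201.5/221/242/256 days and OLEX in about 50/49/47/44% of each arm.

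**3. Formula.** Incidence is the mean over subjects of 1 - exp(-H), where H is the cumulative hazard. With a constant hazard, H = rate × days/365.25. With clustering, a share s of the Day 180 hazard falls in the first 30 days and is repeated in the 30 days after OLEX; the rest is spread evenly over days 31 to 180 and continues at that level. At 0.6 per year, Day 180 incidence is 1 - exp(-0.6 × 180/365.25) = 25.6% in every arm, so the true gap is 0.

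**4. Whole-study incidence (%) at 0.6 per year; gap is 100 U minus 20 U.**

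| Pattern | 20 U | 50 U | 75 U | 100 U | Gap (points) |
|---|---|---|---|---|---|
| Constant | 29.8 | 31.9 | 34.0 | 35.3 | +5.5 |
| s = 0.5 | 32.1 | 33.3 | 34.4 | 35.0 | +2.9 |
| s = 0.8 | 34.0 | 34.3 | 34.5 | 34.5 | +0.5 |
| s = 0.8, full OLEX uptake | 41.7 | 41.9 | 41.7 | 41.2 | -0.5 |
| s = 1 | 35.1 | 34.9 | 34.5 | 34.0 | -1.1 |

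With a constant hazard of 0.3 or 1.0 per year the gap is 3.4 or 6.9 points. With equal durations it is 0. Early clustering is closer to the mild, temporary local reactions described in Protocol 4.3.

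**5. Rare events, constant hazard.** At 0.02 per year, 1.18% against 1.46%, a gap of 0.3 points. At 0.05 per year, 2.92% against 3.61%, a gap of 0.7 points, or 0.007 × 60 = 0.4 of a subject. With s = 0.8 the gap is under 0.1 points.

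**6. Sampling error, 60 against 60 subjects.** 1.96 × sqrt(0.298 × 0.702/60 + 0.353 × 0.647/60) = 16.7 points.

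**7. Level within an arm.** With s = 0.8 and 50% uptake, 100 U shows 27.8% in the main period and 34.5% over the whole study. The difference of 6.7 points carries the 100 U label but follows a 20 U injection. At 20 U the matching difference is 34.0 - 26.2 = 7.8 points.

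**8. Two remedies that do not work alone.** Main-period-only percentages have a larger gap: 5.8 (constant), 3.7 (s = 0.5) and 1.5 points (s = 0.8). Crude main-period rates with s = 0.8 are 0.551 per subject-year at 20 U and 0.465 at 100 U, so 100 U would falsely look 1 - 0.465/0.551 = 16% lower.

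**The case against.** **Redaction.** The first and third TEAE bullets in SAP 7.2.1 have the same visible words, and the third carries a hidden qualifier. With the time-interval analysis named in SAP 7.2, a Day 180 view of all TEAEs may already be planned. This stands. A reader might infer that the plan lacks any time split for all TEAEs; the documents do not support that. No visible text extends such a split to TESAEs or TEAESIs.

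**Related events are covered.** Under Protocol 10.1.2 an event is related if causation cannot be ruled out, so most events caused by the OLEX injection should be classed as related. Those have whole-study, End-of-MP and Day 180 tables for all doses. This stands too, and it narrows the gap. It does not supply TESAE or TEAESI tables regardless of investigator-judged relatedness.

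**Listings suffice.** TESAEs and TEAESIs are listed by subject, and time to onset is listed. With few events a reader could separate them by hand. But time to onset runs from the first administration, so an early post-OLEX event reads as a late event of the Day 1 dose.

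**The protocol asks for the whole study.** True, so those tables should stay.

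**A Day 180 table is not fully like-for-like.** This stands. SAP 7.4.7 gives 10-OCT-2019 as the last randomization. By the SAP 7.1.1 rule for nominal dates, that subject's Day 180 is 10-OCT-2019 + 180 - 1 = 6-APR-2020, after the pandemic assessment of 11-MAR-2020. For late stage 2 subjects V9 could be missed or AEs taken by phone, and no visible text says where the window then closes.

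**Conclusion.** The point holds as a minor, cheap improvement. The rules on period, dose group and end of follow-up combine as described, and the stage 1 interims cannot fill the gap for 100 U and pooled 20 U. What is clearly missing from the visible text is a Day 180 or pre-OLEX window for TESAEs and TEAESIs, and a separate post-OLEX table.

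Under the stated assumptions the spurious 100 U minus 20 U gap runs from about -1 to +7 points for all TEAEs, against about ±16.7 points of sampling error, and is under 1 point for rare events.

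Two stronger readings are tempting. A reader might infer that the tables make the higher doses look worse in a predictable way. They do not: the sign depends on how events cluster after injection and on OLEX uptake, neither of which the documents give. A reader might also infer that a safety conclusion would change. Nothing here supports that, and with equal durations the gap vanishes.

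**What to change.** Keep the protocol-defined whole-study tables. In SAP 7.2.1 add:

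- **(a)** Day 1 to Day 180 tables of TESAEs and TEAESIs, and of all TEAEs unless redacted text already gives them, by Day 1 dose (20 U pooled, 50, 75, 100 U). Exclude events with onset or worsening on or after the OLEX injection. Where V9 was missed or virtual, close the window at a fixed nominal study day by onset or worsening date.
- **(b)** One table of events with onset or worsening on or after the OLEX injection, labelled 20 U OLEX, shown by Day 1 dose and timed from that injection.

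Describe (a) as the comparison with the same nominal follow-up, not as fully like-for-like. Footnote the remaining differences: the ±7 day visit window, early withdrawal, and stage 2 visits missed or held by phone because of COVID-19. Do not rest between-dose statements on main-period-only percentages or crude subject-year rates.

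The cost is a few more tables from dates already collected; for worsened events SAP 6.2.1 already sets "The start date of the AE will be the date of worsening". The primary safety variable is unchanged, so no protocol amendment is needed, and SAP 7.4.2 allows SAP changes for stage 2 before its unblinding. The drawback is that events after Day 180 do not appear in (a).

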7.4 Removal of subjects from treatment or assessment

7.4.1 *Discontinuation of subject's study participation*

In accordance with the Declaration of Helsinki and the informed consent form, the subject may end his/her participation in the study at any time without any penalty or loss of benefits to which the subject is otherwise entitled (see Section 7.4.3). Both the fact and the reason(s) why the subject's participation in the study was prematurely discontinued must be recorded in the source documentation (e.g. subject file) and the electronic case report form (eCRF). Date and discontinuation circumstances should be stated.

The investigator must discontinue the subject's study participation at any time, if any of the following occurs:

- Withdrawal of informed consent.
- Pregnancy prior to injection of IP (in case of pregnancy after a subject has received an injection the subject can continue with applicable study visits until the end of the study but without any invasive procedure, e.g. injections, blood draw, or any other interventional procedure). However the subject is free to discontinue the study at any time.
- Any AE for which treatment continuation would constitute an unacceptably high risk for the subject.

Deviations from this study protocol, or conditions comprising exclusion criteria established in Section 7.3 that arise after the subject has been included in the study may (but will not necessarily) lead to the discontinuation of subject's study participation. All such conditions must be properly documented.

Subjects who discontinue the study because of AEs will be treated according to standard clinical procedures and will be followed up until the End of MP if no optional treatment was received or the OLEX Follow-up Visit V16 if optional treatment was received (see Section 6.1) as described in Section 10.1. All pertinent information concerning the AE will be documented in the source documentation as well as in the eCRF AE report form.

Following discontinuation the End of MP is to be documented. The investigator is required to make every effort to contact subjects lost to follow-up, and all such efforts are to be documented in the source documentation (e.g., times and dates of telephone contact, copies of letters). Please note that subjects who receive optional follow-up treatment but do not attend the OLEX Follow-Up Visit V16 for any reason will not be considered as discontinued prematurely from the study.

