- Section 7.1: More detailed specification of how visits not foreseen in the CSP, which were erroneously performed after V9 and relapse to baseline status, will be handled in efficacy analyses, for several special cases that did not yet occur when SAP version 1.0 was finalized after BDRM for the interim analysis at Month 6 of stage 1.

- Section 7.2: Specification that visits as documented in the eCRF will be used for TEAE incidence by time interval.
- Section 7.2.1: [REDACTED]
Specification that TEAEs related to COVID-19 will be listed only.

- Section 7.4.1: Assumptions regarding and handling of missing values due to COVID-19 pandemic described (including reference to sensitivity analysis in section 7.1.1).
- Section 7.4.7: Statement that and explanation why COVID-19 pandemic could not affect study treatment at Baseline Visit 2 and that an impact of COVID-19 pandemic in terms of

heterogeneity of baseline characteristics of subjects included prior to and during the pandemic can be ruled out.

- Correction of minor typing errors.
- Section 7.1/ 7.1.1/ 7.4.1: Decisions made during the BDRM for the final analysis were added [REDACTED]
[REDACTED]
[REDACTED].
- Section 7.4.6: Conclusion from first BDRM added that no pooling of sites was necessary.

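### SAP 7.2 assigns vital signs, laboratory values and TEAE time intervals by the eCRF label 'End of MP', a visit with no fixed time since injection

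*SAP*

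**What the plan says.** SAP 7.2 states that laboratory values and vital signs "will be analyzed descriptively by treatment and study visit". It then fixes the visit label: "Visits as documented in the eCRF will be used, i.e. visit “End of MP” and not “V15” will be analyzed". The next sentence extends the rule to adverse events: "The same applies to analysis of TEAE incidence by time interval". The change log in SAP 9 lists this extension as deliberate: "Specification that visits as documented in the eCRF will be used for TEAE incidence by time interval".

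On timing, SAP 7.1 says "the End of MP visit is performed between Day 180 ± 7 and 360 ± 7 , depending on when the individual subject relapsed". SAP 3.1 gives the detail. Subjects relapsed by Day 180 finish at Day 180, later relapsers can finish at the visit where relapse is seen, and subjects who never relapse finish at Day 360. Early leavers also use this visit. Protocol 7.4.1 says "Following discontinuation the End of MP is to be documented", and SAP 3.1 asks those who withdraw to attend it.

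The assessment schedules differ. Vital signs are taken at every visit to V9 and then at End of MP (Protocol 9.1.1.6). Blood samples are taken only at screening and End of MP (Protocol 9.1.2.1).

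SAP 7.2.1 lists one table of treatment-related TEAEs up to Day 180 that accepts either V9 or End of MP as the Day 180 visit.

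**The concern.** The event that sets the date of End of MP is relapse, and time to relapse is the primary efficacy variable. If dose prolongs the effect, which is the premise in Protocol 4.3, higher-dose subjects reach End of MP later. A column with that label then shows low-dose subjects mostly near Day 180 and high-dose subjects spread towards Day 360. A difference in vital signs, laboratory values or late TEAEs between doses could reflect time since injection, length of observation or dose, and the table could not tell them apart.

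The V9 column may be affected as well. SAP 7.2.1 treats V9 and End of MP as alternative Day 180 visits, and SAP 7.4.2 had to bring in End of MP visits to complete the Day 180 interim data. Both suggest that subjects relapsed by Day 180 have that visit recorded as End of MP. If labels are used as documented, V9 would hold mainly subjects still in effect, while the relapsers' Day 180 values sit with values up to Day 360.

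Safety is half of the primary objective, so AE timing by dose is an output that readers of this dose-ranging study will look for.

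**Working it through.** The plan gives no figure for this point, so there is nothing to reproduce. The check has two parts: what the text fixes, and an illustration on assumed durations.

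**1. Range fixed by the text.** Nominal: 360/180 = 2.0-fold. With the ±7-day windows: (360+7)/(180−7) = 367/173 = 2.1-fold. Early withdrawals widen it downwards.

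**2. Which outputs are exposed.**

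| Output | Fixed-day columns | Exposed |
|---|---|---|
| Vital signs | V3 to V8 | V9 (selection) and End of MP |
| Laboratory values | none after injection | End of MP, the only post-injection sample |
| TEAE by interval | limits not visible | any interval bounded by End of MP |
| Treatment-related TEAEs to Day 180 | labels merged | not exposed |
| AE tables, entire study period | not visit-based | not exposed |

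**3. Illustration of timing (inputs assumed, not in the documents).** Visits from V9 to V15 are taken as equally spaced: (360−180)/6 = 30 days. End of MP is Day 180 if relapse occurs by then, otherwise the next visit, capped at Day 360. Early withdrawals are ignored.

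Lognormal duration with median m and log-SD 0.35: F(t) = Φ(ln(t/m)/0.35).
- Share at Day 180 = F(180). For m = 120: Φ(0.4055/0.35) = Φ(1.158) = 0.877. For m = 180: Φ(0) = 0.500.
- Share at Day 270 or later = 1 − F(240). For m = 120: 1 − Φ(0.6931/0.35) = 1 − Φ(1.980) = 0.024. For m = 180: 1 − Φ(0.2877/0.35) = 1 − Φ(0.822) = 0.206.
- Mean day = Σ (probability × visit day) = 187 for m = 120 and 218 for m = 180, a gap of about 32 days before rounding.
- With log-SD 0.25 the gap is 209 − 182 = 27 days; with 0.50 it is 229 − 196 = 33 days.

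Weibull duration, S(t) = exp(−ln 2 × (t/m)^k), with wider medians of 120 and 240 days:

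| Shape k | Share at Day 180 (m = 120 / 240) | Mean day (m = 120 / 240) | Gap |
|---|---|---|---|
| 1 | 65% / 41% | 223 / 267 | 44 |
| 2 | 79% / 32% | 193 / 264 | 71 |
| 3 | 90% / 25% | 184 / 260 | 76 |

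**4. Effect on late TEAEs when the true rate is the same in both doses.** With a constant rate r per person-year, the share with a first TEAE after Day 180 and by End of MP is Σ p_v [exp(−180r/365.25) − exp(−vr/365.25)], where p_v is the probability that End of MP is on day v. Over the three Weibull shapes, for m = 120 and m = 240:
- r = 0.25: 0.2–2.5% and 4.6–5.0%.
- r = 1.0: 0.6–5.9% and 11.3–11.7%.

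Up to Day 180 the share is 1 − exp(−180r/365.25) = 11.6% (r = 0.25) or 38.9% (r = 1.0) in both. The late difference comes only from how long subjects are observed, so the denominator matters as well as the interval.

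**5. No dose effect on relapse.** Both groups then have the same p_v, and every gap above is zero. The column still mixes times within each group.

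**The case against.** The case on the other side is substantial.

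- **The interval limits cannot be seen.** A reader might infer that a Day 170 event in one subject and a Day 350 event in another share one interval, or that intervals after Day 180 lose events. The visible text gives no interval limits or denominators, one table descriptor in SAP 7.2.1 is blacked out, and SAP 7.2.3 is not shown. Those specific claims are not supported. The labelling rule itself is visible.
- **The main safety results are untouched.** A reader might infer that the primary AE tables are distorted by this rule. They cover the entire study period and do not use visit labels. Safety analysis is descriptive, without inference (Protocol 12.4.5). This stands, and it limits the point.
- **Timing is not lost.** SAP 7.2 derives time to onset in days and lists it, and the Day 180 table merges the two labels. But the listing is not a summary by dose, and that table covers treatment-related TEAEs only; the visible list has no equivalent for all TEAEs.
- **The label 'End of MP' is more honest than 'V15'.** That is true, since V15 would imply Day 360 for everyone. It does not give the column a time.
- **Laboratory timing comes from the protocol.** With one post-injection sample, no SAP rule can create a common day. This stands.
- **A careless remedy would do harm.** Spreading End of MP vital signs over V10 to V14 would fill those columns only with subjects who relapsed or left at that visit. Splitting laboratory values by day conditions on relapse in the same way. Counting all events from Day 1 would mix in events after the optional retreatment. The remedy has to avoid all three.

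**Conclusion.** The point holds for the by-visit and by-interval safety outputs. As written, SAP 7.2 places observations up to twofold apart in time since injection in one column. It also appears to separate the Day 180 data of relapsers from those of non-relapsers.

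Whether this misleads between doses depends on dose affecting relapse, which the trial is designed to find out. A reader might infer that the dose groups are certain to be compared at different times; the documents support only the conditional statement. On the assumed durations the shift in mean End of MP is about 27 to 33 days for medians of 120 and 180 days, and 44 to 76 days for 120 and 240 days. These figures describe visit timing under assumed inputs, not a measured distortion of any safety result.

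The reading of the V9 column rests on the wording of SAP 7.2.1 and 7.4.2, not on an explicit eCRF rule. The consequence is moderate, and the correction is worth making because it is cheap.

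**What to change.** In SAP 7.2:

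- **TEAEs.** Assign them to fixed study-day intervals from the Day 1 injection, using the time to onset already derived and running to the end of the Day 360+7 window. Use as denominator the subjects still in the main period, and not retreated, at the start of each interval. Report events after the OLEX injection separately.
- **Vital signs.** Combine V9 with any End of MP held at Day 180±7 into one Day 180 column. Show later End of MP values as a last main-period value, with the study-day distribution by dose. Do not spread them over V10 to V14.
- **Laboratory values.** Keep one End of MP column and report its study-day distribution by dose.

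The cost is SAP wording and a derivation from dates already in the data; no new data are needed. The downside is small cells in late intervals, especially for 20 U if its subjects relapse earlier.
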